2.7.2 Secondary objective

Safety:

To evaluate the safety and tolerability the ARGOS-SC pressure during implantation and throughout a 12 months follow-up period.

Performance:

To evaluate the performance of the ARGOS-SC system up to 12 months after implantation.

2.8 Study variables

2.8.1 Primary performance parameters

- GAT measurements (2 3 measurements) at visit V02 V09
- ARGOS-SC system measurements (2 3 measurements) at visit V02 V09 roughly contemporaneous with the GAT measurements
- Pascal DCT (2 3 measurements) at visit V05 V09 (if available)
- ARGOS-SC system measurements (2 3 measurements) at visit V05 V09 roughly contemporaneous with the Pascal DCT measurements

2.8.2 Safety parameters

- Device deficiency / device malfunction
- Adverse events (AE / ADE / SAE / SADE)

2.8.3 Further ophthalmological parameters

- 24-hours measurements inpatient with GAT and ARGOS-SC every 3 hours at visit V06, V07 and V09.
- User acceptance questionnaire for surgeon (7 items) at visit V01
- User acceptance questionnaire for investigator (24 items) at visit V09
- User acceptance questionnaire for patient (16 items) at visit V09
- Visual acuity (subjective and objective refraction, best corrected visual acuity on study eye at Screening and Visit V02 – V09
- Perimetry: Visual field on both eyes at Screening and visit V06, V07, and V09
- The ANTERION® from Heidelberg Engineering performed: no / yes at V04 V09
- Anterior eye segment measurement on study eye:
 - Optical coherence tomography (OCT), Central cornea thickness (CCT) at Screening and visit V04 – V09
 - Slit-lamp biomicroscopy (Lids, Conjunctiva, Cornea, Anterior chamber, Iris Pupil, Lens, Anterior vitreous body) at Screening and visit V02 V09
 - Gonioscpoy (angle open to (Shaffer), pigmentation of Trabecular meshwork)

- Posterior eye segment measurement:
 - Biomicroscopy (dilated, fundus) on study eye at Screening and visit V02 V09
 - Optical coherence tomography (OCT) on both eyes at Screening and visit V06, V07, and V09

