9.1.3 Safety Analysis

The incidence and nature of adverse events observed within the safety population will be analyzed by descriptive and explorative statistical methods.

Safety will be described in detail by frequency, seriousness, severity, nature and duration of events. Number of adverse events as well as the number and relative frequency of patients reporting adverse events will be tabulated by system organ class and preferred terms. The same table will be prepared for serious adverse events. In addition, the number and relative frequency of patients reporting adverse events will be tabulated by system organ class and preferred terms in dependence on the worst severity and worst causal relationship. Furthermore, number of adverse device effects as well as the number and frequency of patients reporting adverse device effects will be tabulated by system organ class and preferred terms and not by event description as stated in the protocol.

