3.1 Responsibility

All tables, graphics and listings, and the statistical analysis will be produced by *CRO Dr. med. Kottmann GmbH & Co. KG*. The reconditioning / coding of diseases and drugs will be conducted by *Implandata Ophthalmic Products*.

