3.5 Descriptive statistics

Descriptive statistics calculated for continuous variables will be

- number of patients
- number of valid patients
- mean
- standard deviation
- minimum
- maximum
- median
- percentiles (if indicated)

All continuous parameter will be tested for normal distribution by using Shapiro-Wilk-Test.

For categorical variables

- number of patients
- number of valid and/or missing values
- absolute frequencies (n)
- relative frequencies (%)

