4.2 Definition of baseline and endpoints, and derived variables

Baseline values are determined in the Screening visit before the implantation procedure.

Post values are defined as the values after the implantation procedure.

Change from baseline (Δ) is defined as the difference between the baseline value obtained before implantation procedure and the post value after implantation procedure separately for each visit:

 Δ = Post value - Baseline value

Percent change from baseline is defined as the change from baseline divided by the baseline value times 100%:

 $\%\Delta$ = ((Post value - Baseline value) / (Baseline value)) x 100

In case of measurements / assessments before (pre) and after (post) implantation the change from baseline and the percent change from baseline (if indicated) will be calculated.

In case of ordinal scales, shift tables (before vs. after) may be used instead of differences.

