4.6.2 Safety endpoints

Incidences of adverse events stratified by:

- expectedness: expected event / unexpected event (N, %)
- severity: mild / moderate / severe (N, %)
- causal relationship to medical device: none / unlikely / possible / probable / definite (N, %)
- causal relationship to other: none / unlikely / possible / probable / definite (N, %)
- seriousness: yes / no (N, %)
- outcome: recovered / recovered with sequelae / recovering / not recovered / death / unknown (N, %)

(if indicated).

Incidences of device deficiency stratified by:

- involved component: ARGOS-SC sensor / MESOGRAPH reader (N, %)
- did this device deficiency involve the patient: no / yes (N, %)
- consequences of the device deficiency (ARGOS-SC sensor): none / recalibration / discontinued use / explanation (N, %)
- consequences of the device deficiency (MESOGRAPH reader): none / discontinued use / discontinued use with a replacement device (N, %)

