4.6.3 Further endpoints

- User acceptance of the ARGOS-SC implantation procedure by means of evaluation of implantation procedure questionnaires (investigators) at V01 (statistical parameters)
- User acceptance of the ARGOS-SC system at the investigational site by means of evaluation of patient acceptance questionnaires (by investigators) at V09 (statistical parameters)
- User acceptance of the ARGOS-SC system at home by means of evaluation of patient acceptance questionnaires (patients) at V09 (statistical parameters)
- Repeatability of the ARGOS-SC measurement (statistical parameters)
- Concomitant glaucoma medication is shown separately as follows:
 - Previous glaucoma medication (stopped before implantation): in total (N,%) and stratified by ingredients (N, %) (Mock-up Table 3a)
 - Concomitant glaucoma medication (medication given during V01 V09): in total (N, %) and stratified by ingredients (N, %) (Mock-up Table 3b)

- Other concomitant medication is shown separately as follows:
 - Previous medication (stopped before implantation): in total (N, %) and stratified by ingredients (N, %)
 - Concomitant medication (medication given during V01 V09): in total (N,
 %) and stratified by ingredients (N, %)
- NEI VFQ-25 questionnaire:
 - 25 items in course of study (statistical parameters)
 - 12 sub-scales in course of study (statistical parameters)
 - Changes from baseline of the 12 sub-scales (statistical parameters)

The changes from baseline of the 12 sub-scales will be analysed by means of paired t-Test (in case of normal distribution) or the Wilcoxon sign rank test (in case of non-normal distribution). The Mixed Model repeated measurement (MMRM) analysis of covariance for repeated measures in mixed models (V06, V07, V09 vs. Screening) will be used in addition.

 Daily IOP self-measurement profiles (patients) will not be included into the evaluation.

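### Study-eye visual acuity reaches the analysis only through generic per-visit summaries, which do not show how many eyes had a relevant loss or whether the same eyes kept it

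*SAP*

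**What the plan says.** Best corrected acuity is measured by the ETDRS procedure at Screening and at all eight follow-up visits (protocol Table 1). Characters read and reading distance are recorded (protocol 8.3.13.8), so letters lost can be computed. SAP 2.8.3 carries this over as "best corrected visual acuity on study eye at Screening and Visit V02" to V09.

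Acuity is not named in the SAP's safety parameters (2.8.2), endpoints (2.9), analyses (4.6.1 to 4.6.3) or mock-up tables (section 5). Two general rules reach it:

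- SAP 3.5 gives counts, mean, SD, minimum, maximum and median for continuous variables, with percentiles where indicated.
- SAP 4.2 applies generally: "In case of measurements / assessments before (pre) and after (post) implantation the change from baseline" is calculated, separately for each visit. Shift tables are optional and only for ordinal scales.

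SAP 3.1 mentions listings in general terms ("All tables, graphics and listings, and the statistical analysis will be produced by" the CRO), but none is defined for acuity. The protocol's safety analysis (9.1.3) is built on adverse events: "Safety will be described in detail by frequency, seriousness, severity, nature and duration of events".

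**The concern.** Safety and tolerability is a secondary objective of a first-in-human study of an implant meant to stay in the eye permanently. For vision, the useful questions are how many study eyes lost a meaningful number of letters, which eyes they were, and whether the loss lasted. A mean, SD and minimum at each visit answer none of these fully. The minimum shows one eye, and tables made separately for each visit do not follow an eye from one visit to the next.

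The adverse-event route covers loss that someone reports. Neither document states an acuity change that must be recorded as an event. The only visual item among the adverse events of particular interest (protocol 7.3) is temporary impairment secondary to the other listed events. An eye with measured loss and no matching event would therefore be hard to see in the planned output.

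**Working it through.** The plan gives no acuity threshold, rate or power figure to reproduce. The check asks whether the planned summaries determine the number of eyes with loss, or its persistence.

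**Inputs.** 24 patients, one study eye each (protocol 8.3.7). Summaries as in SAP 3.5 with quartiles, which the mock-up tables show. Assumed: thresholds of 10 and 15 letters, the invented letter changes below, and equal Screening acuity in all eyes, so that raw and percent-change summaries also match.

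**Two data sets for one visit.** Both share 18 eyes: -3, -3, -2, -2, -1, -1, 0, 0, 0, 1, 1, 2, 2, 3, 3, 4, 5, 6 (sum 15, sum of squares 133). The other six are:

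- Set A: -20, -19, -9, -9, -8, -4. Sum -69; sum of squares 400 + 361 + 81 + 81 + 64 + 16 = 1003.
- Set B: -20, -15, -15, -11, -4, -4. Sum -69; sum of squares 400 + 225 + 225 + 121 + 16 + 16 = 1003.

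Both sets then have sum 15 - 69 = -54 and sum of squares 133 + 1003 = 1136.

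- Mean = -54/24 = -2.25.
- SD = sqrt((1136 - 54²/24)/23) = sqrt(44.11) = 6.64.
- Minimum -20, maximum 6.
- Quartiles from ranks 6/7, 12/13 and 18/19: (-4 - 3)/2 = -3.5, (-1 + 0)/2 = -0.5, (2 + 2)/2 = 2.

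The summary tables are identical, but the counts are not (exact Clopper-Pearson 95% intervals):

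| Loss | Set A | Set B |
|---|---|---|
| ≥10 letters | 2/24 = 8.3% (1.0% to 27.0%) | 4/24 = 16.7% (4.7% to 37.4%) |
| ≥15 letters | 2/24 = 8.3% (1.0% to 27.0%) | 3/24 = 12.5% (2.7% to 32.4%) |

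**All integer data sets with that table.** Full enumeration of ordered whole-letter vectors with this n, minimum, maximum, sum, sum of squares and quartiles gives 2 to 5 eyes at ≥10 letters and 1 to 3 at ≥15. With only the median fixed, the ranges are 1 to 7 and 1 to 3. The two thresholds can rank data sets differently: 5 eyes at ≥10 with 1 at ≥15 fits the table, and so does 2 with 2. That is why both thresholds are useful.

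**Persistence.** Let set B occur at both V08 and V09. If the same four eyes are affected each time, 4/24 have lasting loss. If four different eyes are affected at each visit, eight eyes are affected and 0/24 have lasting loss (interval 0% to 14.2%). The V08 and V09 tables are the same in both cases.

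**The case against.** The strongest reply is that the protocol already has a route for the loss that matters most. Permanent impairment of a body function, with serious deterioration, makes an event serious (11.2.2). Untoward clinical signs and directly observed events count as adverse events (11.2, 11.3). Any SAE must be reported whatever its relationship to the device, and doubtful cases are reported as if serious (11.4). The investigator examines the patient at each follow-up visit and records clinically significant anomalies (8.3.11). Events are tabulated by severity, seriousness and outcome (SAP 4.6.2). A DSMB of independent clinicians reviews the safety data, not only device-related events (11.7). Data management queries questionable values (10.3). All of this stands, and it narrows the gap to measured loss that was not reported or was judged not serious.

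Three further replies have some force. Acuity is not a protocol endpoint, so the SAP departs from nothing. The example is constructed, and any continuous variable summarised by visit has the same property. SAP 3.5 allows other percentiles, and the 10th percentile would separate the two sets (-9 in A, -15 in B). That last option is discretionary, however, and no percentile links an eye across visits.

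A reader might infer more: that lasting visual loss has no reporting route, that harm from the implant would be hidden, or that the SADE criterion in protocol 9.5 cannot be trusted. The documents do not support these readings. The first is answered by 11.2.2 to 11.4. On the second, there is no control group (8.1.2), and 7.3 says relationship to the implant cannot be independently assessed, so an acuity table could not settle attribution either. On the third, SADEs are evaluated by the DSMB, and a letter count does not verify that evaluation.

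**Conclusion.** The point holds in a limited form. Per-visit summaries and change from baseline leave open how many eyes had a relevant acuity loss and whether the same eyes kept it. The adverse-event system covers reported loss, including lasting serious loss. The remaining gap is measured loss that went unreported or was judged not serious.

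The weight is minor: no primary result, pass/fail rule or SADE count changes. The conclusion that the summaries are insufficient follows from their form. The sizes (2 to 5 eyes, 1 to 3 eyes, 4/24 against 0/24) rest on invented data and assumed thresholds. They show what the tables leave undetermined, not a likely result, and intervals at 24 eyes are wide.

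**What to change.** In SAP 4.6.2, on the safety set:

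1. **Table.** For each visit V02 to V09, give n (%) of study eyes losing at least 10 and at least 15 ETDRS letters from Screening, as description only. The denominator is eyes assessed at both time points. The documents give no thresholds, so state these as assumptions and fix them before database lock. Use the letter score with the recorded reading distance taken into account.
2. **Listing.** For every eye meeting a threshold at any visit, list acuity at all visits beside its recorded AEs, SAEs and SADEs. Mark loss as lasting if present at both V08 and V09, or otherwise at the last two attended visits from V06 onward. Mark eyes without two such visits as not assessable.
3. **Statement.** Say that the table does not attribute loss to the implant.

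The cost is one table and one listing from data already collected, plus the programming to match acuity with events. The downside is that early postoperative loss expected from the glaucoma surgery will appear and need comment. Some early leavers will also be not assessable for lasting loss.

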2.8.4 Further study variables

- Inclusion criteria at Screening
- Exclusion criteria at Screening
- Demographic data at Screening
- Educational level at Screening
- Medical history at Screening
- · Glaucoma anamnesis at Screening
- Previous glaucoma medication (stopped before implantation) (Mock-up Table 3a)
- Concomitant glaucoma medication from V01 V09 (Mock-up Table 3b)
- Other previous medication (stopped before implantation)
- Other concomitant medication from V01 V09
- Pregnancy test (for female subjects of childbearing potential) at Screening and before surgery
- Surgery related data (study eye, examination prior surgery, ARGOS-SC implantation, Intraocular lens implantation, complications)
- Visual Function Questionnaire (VFQ-25) at Screening and visit V06, V07, and V09

2.9 Study endpoints

2.9.1 Primary endpoints

Performance:

Level of agreement between measurements made using GAT and the ARGOS-SC system at visit V02 - V09.

The concordance of the intraindividual measurement values of GAT and ARGOS-SC will be indicated by the concordance correlation coefficient r_{ccc} (4.6.1), separate for each visit

Additionally, the absolute difference between the GAT and ARGOS-SC measurement will be scaled in \leq 5mmHg and > 5 mmHg and the frequency distribution will be displayed (4.6.1, Table 2).

The Bland-Altman (mean-difference) plot and a X-Y plot should illustrate the comparison of the two methods (4.6.1, Figure 1).

The level of agreement between Pascal DCT and ARGOS-SC will be evaluated analogously.

2.9.2 Secondary endpoints

Safety:

- Number of patients experiencing a device-related SAE (SADE) at any time during implantation and in the first 12 months (day 0 to day 360) following it.
- Incidence, nature, severity and seriousness of observed adverse events (AE) and adverse device events (ADE) at any time during implantation and in the 12 months following it.

Performance:

- Repeatability of the ARGOS-SC measurement.
- Comparison of OPA measurements with the repeatability of the ARGOS-SC measurement
- Incidence, nature and seriousness of observed device malfunctions during implantation and in throughout a 12 months follow-up period.

Utility:

- User acceptance of the ARGOS-SC implantation procedure by means of evaluation of implantation procedure questionnaires (surgeon)
- User acceptance of the ARGOS-SC system at the investigational site by means of evaluation of patient acceptance questionnaires (by investigators)
- User acceptance of the ARGOS-SC system at home by means of evaluation of patient acceptance questionnaires (patients)

2.9.3 Further endpoints

NEI VFQ-25 questionnaire:

The 25 items will be converted to a 0 (= worst response) to 100 scale (= best response). Then, the items within sub-scale will be averaged to create 12 sub-scale scores:

- General health (1 item: question 1)
- General vision (1 item: question 2)
- Ocular pain (2 items: question 4 and 19)
- Near activities (3 items: question 5, 6, and 7)
- Distance activities (3 items: question 8, 9, and 14)
- Vision specific: Social functioning (2 items: question 11 and 13)
- Vision specific: Mental health (4 items: question 3, 21, 22 and 25)
- Vision specific: Role difficulties (2 items: question 17 and 18)
- Vision specific: Despendency (3 items: question 20, 23 and 24)
- Driving (2 items: question 15c, 16)
- Color vision (1 item: question 12)
- Peripheral vision (1 item: question 10)

2.10 Study Flow Chart

Visit	SC	V01	V02	V03	V04	V05	V06	V07	V08	V09
Indicative Days (D) Visit window	Up to 28 days before surgery	D0	D1	D3 - 1/+ 2 days	D10 +/- 1 day	D30 +/- 5 days	D90 +/- 10 days	D180 +/- 15 days	D270 +/- 15 days	D360 +/- 15 days
GENERAL										
Informed consent signed	Х									
Allocation of subject number	Х									
Inclusion & exclusion criteria	Х	X¹								
Demography	Х									
Past and current significant medical history	х									
Pregnancy test (urine beta-hCG)	Х	X ²								
Non-penetrating glaucoma surgery and ARGOS-SC pressure sensor implantation		×								
Vision related Quality of Life (VFQ-25) questionnaire	Х						Х	Х		Х
Visual acuity (ETDRS) ³	Х		Х	Х	Х	Х	Х	Х	Х	X
Perimetry ⁴ (OU)	X						Х	Х		X
Heidelberg Engineering ANTERION®					Х	Х	Х	Х	Х	X
External eye photography ⁵	Х				Х	Х	Х	Х	Х	Х
Implantation procedure questionnaire (surgeon)		Χ								
User acceptance questionnaire (patient)										X
User acceptance questionnaire (investigator)										Х
Concomitant medication	×	Х	Х	Х	Х	Х	Х	Х	Х	X
AE/ADE/SAE/SADE		Х	Х	Х	Х	Х	Х	Х	Х	Х
Device malfunction		Χ	Х	Х	Х	Х	Х	Х	Х	Х
ANTERIOR SEGMENT										
Optical Coherence Tomography ⁶	Х				Х	Х	Х	Х	Х	Х
Slit-lamp biomicroscopy ⁷	Х		Х	Х	Х	Х	Х	Х	Х	Х
Gonioscopy ⁹	Х						Х	Х		X

POSTERIOR SEGMENT										
Slit-lamp biomicroscopy ⁹	Х		Х	Х	Х	Х	Х	Х	Х	Х
Optical coherence tomography (OCT) ¹⁰ (OU)	Х						Х	Х		Х
Fundus photography ¹¹	Х						Х	х		Х
Goldmann Applanation Tonometry ¹²	Х		Х	Х	Х	х	Х	Х	Х	Х
Pascal Dynamic Contour Tonometry ¹²	Х					x	х	Х	х	X
ARGOS-SC pressure sensor measurement ¹²			Х	Х	Х	х	Х	Х	х	Х
24-hours measurements inpatient with GAT and ARGOS-SC over 24h ¹³							×	Х		X
ARGOS-SC pressure sensor self- measurement ¹⁴		Х	x	×	Х	×	X	х	×	X

¹ Eligibility must be reassessed at V01 prior to surgery.

- ⁸ Slit-lamp biomicroscopy is performed through an undilated pupil to assess the following anatomic parameters of the anterior segment: lids, conjunctiva, cornea, anterior chamber, iris, pupil, lens and anterior vitreous body.
- ⁹ Standard gonioscopy is used to confirm glaucoma classification and to evaluate the presence of iris tumors, foreign bodies, anterior synechiae and to predict the anterior chamber angle. The gonioscopic grading system according to Shaffer is used in this clinical investigation.
- ¹¹ Posterior segment biomicroscopy is performed by means of indirect ophthalmoscopy on a slit lamp with the aid of a 90D or "Superfield" or comparable lenses. For this examination the pupil needs to be dilated by the use of mydriatic agents. This method is used to evaluate the following parameters: optic nerve lesions, other posterior pole lesions, vitreous opacities, optic nerve head, fundus lesions, retinal arteries and veins (AV), macular area, fundus periphery, normal and abnormal variations of the fundus.
- ¹² Posterior segment OCT is used to assess macular structures and the peripapillary nerve fiber layer thickness (RNFLT) and if possible Minimum rim width at Bruch membrane opening (BMO-MRW).
- ¹³ The fundus should be photographed in order to document potential changes to the optic nerve (cup/disc ratio) and nerve fiber layer (redfree illumination)
- ¹⁴ V02 to V09 IOP measurements will be made in series of 2 GAT measurements (in case of a difference of more than 2 mmHg, a third GAT measurement is required) followed by 3 directly consecutive ARGOS-SC system measurements; if DCT is available: V05 to V09 additionally followed by 2 Pascal DCT measurements (in case of a difference difference of more than 2 mmHg, a third Pascal DCT measurement is required) and 3 directly consecutive ARGOS-SC system measurements.
- ¹⁵ Patient's admission at the site for a 24h series of measurements with GAT and ARGOS-SC sensor. Measurements with EYEMATE-SC sensor will be done automatically via an externa antenna. GAT will be done every three hours, if it is possible even at night. If night measurements are not possible every three hours at night, the last measurement should take place between 22 and 24 o'clock and the three-hours rhythm should be resumed between 5 and 7 o'clock on the next morning.
- ¹⁶ All patients will receive a MESOGRAPH reading device after implantation in order to measure the IOP daily at home. Measurements will be taken at least 4 times per day (morning, noon, afternoon, evening). The MESOGRAPH reading device will be connected to an external GSM module, which will transfer the measured value directly to a secure database. Investigators can log into the database in order to track the pressure levels of their patients as required.

² For females of childbearing potential, a pregnancy test performed within 24 hours preceding surgery must be negative to confirm eligibility.

⁴ The best corrected visual acuity will be determined after objective and subjective determination of refraction with the ETDRS chart in accordance with the ETDRS protocol.

⁵ Perimetry is performed to obtain an accurate examination of the peripheral extent of the visual field. Automated perimeters will be used either with standard glaucoma field, field 30-2 or equivalent.

⁶ External eye photography is performed through a slit lamp camera or equivalent. The outer eye shall be photographed in order to document potential changes to the iris or pupil structure.

⁷ Anterior segment OCT is performed to evaluate effects on change in chamber angle after non-penetrating glaucoma surgery and to assess corneal thickness.

3 General Considerations

